Inclusion and Exclusion Criteria

(1) **Screening.** Using an existing collaboration with the CMSD school system, participants will be recruited via advertisements in parent meetings at CMSD schools and social media. Candidates whose parents indicate interest by phone call, email, message, or completing an online prescreening tool will be contacted using an IRB approved script to recruit, screen, and enroll participants. Adolescents will complete the PHQ-8 measure of depressive symptoms over the phone or by REDCap link on a tablet computer. A PHQ8 score >8 and <20 will be considered for study inclusion. Screening the adolescent with the PHQ8 confirms that the adolescent currently has moderate depressive symptoms and will occur during the screening process, prior to consent/assent. We have requested a waiver of consent on page 7 for screening purposes.

(2) Inclusion (adolescent)	
1.	A Cleveland Metropolitan School District student
2.	Ages 14-17 years old
3.	Reports diagnosis of depression
4.	Reports moderate depressive symptoms (PHQ-8 score >8 and <20)
5.	Able to read, speak, and understand the English language
Inclusion (parent/guardian)	
1.	Female parent/guardian
2.	Able to read, speak, and understand the English language

(3) Exclusion (adolescent)	
1.	Current suicide risk
2.	Diagnosis with bipolar disorder, schizophrenia, or a personality disorder
3.	Sever behavioral problems that preclude group participation (as reported by parent)
4.	Family plans to move from the region within one year
Exclusion (parent)	
1.	Family plans to move from the region within one year

Number of Research Participants

(1) N = 30 adolescent/parent dyads
 (2) Single site study, N/A

Vulnerable Populations

(1) Vulnerable populations included are:

- Adults unable to consent**
- Minors (infants, children, teenagers)**
 - Wards of the state
 - Foster Children
- Pregnant Women**

- Neonates**
- Employees of CWRU or UHHS**
- Prisoners**
- Illiterate Individuals**
- Non-English Speaking**
- University Students**

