(2) Minors will be recruited with permission of the parent/guardian during the process of informed consent with assent designated for acceptance by the minor. Minors are the participant of interest, since this is a pediatric study targeting adolescent participants with depression. The consent/assent document was designed with adolescents in mind, including simple and clear lay language to promote respect for (minor) persons with shared consent/assent decision-making between parent and adolescent. Drs. [name] and [name] have conducted previous research protocols that involve adolescent-parent dyads and have experienced research assistants and established protocols for quality assurance, crisis intervention and referral, as well as initial and ongoing staff training. The research assistants hired for this project will have prior experience working with adolescent-parent dyads.

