Risks associated with study procedures (surveys, behavioral interaction, RSA) are not greater than encountered in daily life and will be minimized with careful attention to adolescent participant needs. There is the potential for stigmatization due to depression diagnosis; however, measurements are taken in private and all results are reported privately in a sensitive and culturally appropriate manner. If questionnaires indicate symptoms suggestive of severe depression or suicidal ideation, the results will be reviewed with [name], Ph.D. (co-investigator, licensed clinical psychologist, #6732) who will consult with the adolescent and/or parent/guardian to determine whether the adolescent or parent/guardian is in need of a referral for further evaluation and treatment. The nature of this study includes adolescents with a diagnosis of depression. If the adolescent becomes upset during study procedures, a study research assistant and the participant's parent will be available to support and comfort the adolescent participant if needed. The adolescent/parent dyad will be given an information sheet with the number of United Way First Call (211) to access on call mental health professional services in their local area or Cuyahoga County 24-Hour Mental Health Crisis Information and Referral [contact]). If the participant is unable to be comforted by the research assistant or the parent and further assistance is required, the Mobile Crisis Team from the Cuyahoga County 24-Hour Mental Health Crisis, Information, and Referral Hotline will be contacted immediately. In addition, our Data and Safety Monitoring Committee (DSMC) will include an individual with expertise and experience conducting research studies with minor participants.

(3) Pregnant women are not targeted for inclusion in this study, but will not be excluded in this study. Non-English speaking individuals will be excluded in this study. At this time, our study does not have the means to accommodate non-English speaking participants. This is a small (N=30), proof of concept, pilot study conducted by an early stage investigator. Once our team has evidence that trust-building interventions are effective, we will expand our reach with larger studies, which will include non-English speaking families.

Recruitment Methods

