b. **Questionnaires:** Survey data will be collected using REDCap on a tablet computer. Measures used in the study are listed in the Table below. Due to restrictions associated with the COVID-19 pandemic, parents and adolescents will be asked to answer questions privately and at approximately the same time point on an electronic device connected to the internet in their homes. If, for example, only one electronic device is able to connect to the internet, the adolescent can complete the survey and then pass the device to the parent for survey completion. We are assessing families for internet access and device availability in the screening form. For families that do not have a device, we will mail them a tablet that they will mail back to us at the end of the study.

Study Variables, Measures, and Data Collection Points						
ADOLESCENT SURVEY						
Variable	Instrument	Title on Survey	B	3M	6M	
Depressive symptoms	Patient Health Questionnaire-8 ¹⁹	Depression Questions	X	X	X	
Quality of life	Youth Quality of Life-Short Form ²¹	Quality of Life Questions	X	X	X	
Sleep	PROMIS sleep disturbance-4 ²⁵ Children's Report of Sleep Patterns ²²	Sleep Questions More Sleep Questions	X X	X X	X X	
Stress management	Adolescent Lifestyle Questionnaire—stress management subscale ²³	How do you handle your stress?	X	X	X	
Medication adherence	Extent of Medication Adherence ²⁴	Medication Questions	X	X	X	
Appointment keeping	Hill-Bone Compliance Scale ²⁵	Appointment Questions	X	X	X	
Biologic Trust	Respiratory sinus arrhythmia ¹³	Not applicable—assessment in lab	X	X		
Behavioral Trust	Behavioral interaction assessment ¹⁴	Not applicable—assessment in lab	X	X		
Cognitive Trust	Children's General Trust Scale ²⁶	Children's Trust Questions	X	X	X	
Cognitive Trust	Parent Trust of Child Scale—Adolescent perceived ²⁷	Parental Trust Questions	X	X	X	
Relationship quality	Inclusion of Other in Self ²⁸	How close are you with your parent?	X	X	X	
Self-regulation	Positive and Negative Affect Schedule ²⁹	Emotion Questions	X	X	X	

Family cohesion	Brief Family Relationship Scale ³⁰	Family Relationship Questions	X	X	X
Rumination	Children's Response Style Questionnaire ³²	How do you handle sadness?	X	X	X
Self-efficacy	PROMIS Self-efficacy - Youth ³¹	Getting stuff done questions	X	X	X
Decentering	Experiences Questionnaire ³³	Self-awareness Questions	X	X	X
Demographics	Demographics questionnaire	Who are you?	X		
Perceived stress	Perceived Stress Scale-Peds ³⁴	Stress Questions	X	X	X

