COVID anxiety	COVID anxiety-5	COVID anxiety	X	X	X
Anxiety symptoms	PROMIS-25 Pediatric ¹⁹	Health Questions	X	X	X
Executive function	Pediatric Cognitive Function Short Form ³⁵	Thinking Questions	X	X	X
Parenting monitoring	Parental Monitoring Scale ³⁶	How much do your parents keep an eye on you?	X	X	X

PARENT SURVEY

Biologic Trust	Respiratory sinus arrhythmia ¹³	Not applicable—assessment in lab	X	X	
Behavioral Trust	Behavioral interaction assessment ¹⁴	Not applicable—assessment in lab	X	X	
Cognitive Trust	Parent Trust of Child Scale—Parent ²⁷	Parent's Trust of Child Questions	X	X	X
Relationship quality	Inclusion of Other in Self ²⁸	How close are you with your teen?	X	X	X
Relationship quality	Parent-Child Coercion Scale ³⁷	Parent-Child Communication Questions	X	X	X
Demographics	Demographic questionnaire	Who are you?	X		
Parenting style	Alabama Parenting Questionnaire-Shor ³⁸	Parenting Style Questions	X	X	X
Parent stress	PROMIS Perceived Stress Scale ³⁴	Stress Questions	X	X	X
General health	PROMIS-25 ¹⁹	General Health Questions	X	X	X

Note. B = baseline, 3M = 3 months, 6M = 6 months

We are also providing families with information about free or reduced cost internet access and free internet hot spots in the community (attached). Once restrictions associated with the COVID-19 pandemic are eased, in-person data collection will resume. Parent and adolescent will simultaneously answer questions on separate computers in a private room. This is intended to allow both to answer questions privately and to prevent parents from interfering with adolescent responses. During social distancing due to novel coronavirus-19, we will email a link to the questionnaire to participants. All materials will be assigned a unique number that will be used to link data over time. A master list linking the ID number to the participant's name will be kept in a password-protected computer file, in a locked office, at the local site. This list will be kept entirely separate from the data so that responses cannot be linked to the individual participant.

c. The risks associated with gathering information from participants by properly trained and supervised research assistants are low. Participants may experience discomfort by

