some questions assessing stress and depression. In prior research, we have used these measures or similar measures with this adolescent-parent dyad population and found that adolescent-parent dyads were comfortable with the interviews. However, all participants will be instructed that they can stop the interview at any time or can choose to skip any question that they wish. Our investigators and staff are experienced interviewers in research involving adolescent-parent dyads, and we have rarely encountered participant reactions more adverse than transient awkwardness, embarrassment, or mild discomfort. If questionnaires indicate symptoms suggestive of severe depression or suicidal ideation, the results will be reviewed with [name], Ph.D. (co-investigator, licensed clinical psychologist, #6732) who will consult with the adolescent and/or parent/guardian to determine whether the adolescent or parent/guardian is in need of a referral for further evaluation and treatment. The nature of this study includes adolescents with a diagnosis of depression. If the adolescent becomes upset during study procedures, a study research assistant and the participant's parent will be available to support and comfort the adolescent participant if needed. The adolescent/parent dyad will be given an information sheet with the number of United Way First Call (211) to access on call mental health professional services in their local area or Cuyahoga County 24-Hour Mental Health Crisis Information and Referral [contact]). If the participant is unable to be comforted by the research assistant or the parent and further assistance is required, the Mobile Crisis Team from the Cuyahoga County 24-Hour Mental Health Crisis, Information, and Referral Hotline will be contacted immediately.

- d. **Cheek swab DNA test:** The cheek swab DNA test is canceled due to COVID-19. The cheek swab DNA test includes swabbing the parent and adolescents' cheek with separate sterile cotton swabs. Participants can remain in the study, but opt out of the DNA test, if they choose. Participants will be assured that we will not use the data for paternity testing. The sensation of a cotton swab in the mouth may feel uncomfortable for some. We will allow participants to swab their own cheek under guidance of study staff, if they prefer.

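### The protocol promises psychologist review when questionnaires indicate suicidal ideation, but identifies no measure that asks about it and sets no time for reading emailed surveys

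*Combined protocol and SAP*

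**What the plan says.** The safety commitment opens "If questionnaires indicate symptoms suggestive of severe depression or suicidal ideation" and then sends the results for review with the co-investigator who is a licensed clinical psychologist. That person then decides with the family whether a referral is needed. It appears in Vulnerable Populations (2), in Study Design, Procedures, and Timeline (item c), and twice in Risks to Research Participants (under 1 and 5).

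On what the questionnaires are, Study Design item b says: "Measures used in the study are listed in the Table below". In that table depressive symptoms are measured by the "Patient Health Questionnaire-8" at baseline, 3 and 6 months. The table gives variables, instrument names and survey titles, but no items.

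On delivery, item b says that during social distancing "we will email a link to the questionnaire to participants", and the surveys are completed at home.

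On entry, the screening paragraph says: "A PHQ8 score >8 and <20 will be considered for study inclusion". Current suicide risk is listed as an adolescent exclusion, with no method of assessment. The planned size is "N = 30 adolescent/parent dyads".

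The protocol also relies on "established protocols for quality assurance, crisis intervention and referral" (Vulnerable Populations; Risks to Research Participants), whose content is not reproduced.

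**The concern.** A review that starts from questionnaire answers needs a question that can produce the answer. The severe-depression half of the trigger has an identifiable measure, the PHQ-8. The ideation half has none that the protocol points to. If no survey question asks, staff cannot read ideation from the answers, however carefully they look. If a question does ask, an answer sent from home still helps only once someone reads it, and no one is given a time for that.

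The participants are 14 to 17 years old, report a depression diagnosis and have moderate symptoms. The protocol itself treats ideation as foreseeable enough to need a clinician. What is at stake is participant safety between entry and 6 months. Estimation and interpretation of the trial are not affected.

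**Working it through.** There is no plan figure to reproduce. The check is a count of what the protocol identifies, followed by a comparison of its safety provisions.

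**1. The trigger.** Vulnerable Populations (2) 1 + Study Design item c 1 + Risks to Research Participants 2 = 4 statements. Statements naming an item: 0. Statements giving a review time: 0.

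**2. The measures table.**
- Adolescent rows: 22. Two are laboratory assessments (respiratory sinus arrhythmia and behavioural interaction), so 22 − 2 = 20 questionnaire rows.
- The sleep row names two instruments, so 20 + 1 = 21 adolescent instruments.
- Parent rows: 9, of which the same two are laboratory assessments, so 9 − 2 = 7 questionnaire rows.
- Rows whose variable, instrument name or survey title identifies suicidal ideation or self-harm: 0 of 20 adolescent and 0 of 7 parent.

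This counts what the protocol identifies. It is not a count of item content.

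**3. The stated times, and what each covers.**
- Immediate call to the mobile crisis team (Vulnerable Populations; Study Design item c): a participant upset during procedures who cannot be comforted.
- Immediate report to the investigator (Provisions to Monitor the Data): an adverse or unanticipated event, once it is known.
- Three business days and two weeks (same section): reports to the IRB and the sponsor.
- Reading of survey answers that arrive through the emailed link: no time stated.

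**4. The other safeguards, and whether each is stated to ask about ideation.**
- Entry exclusion for current suicide risk: considered before enrolment, method not stated, and not stated to be repeated at 3 or 6 months.
- Conversation at each study visit (Consent Process): the examples ask how the study is going and whether it is understood, not about ideation.
- Distress support and crisis numbers (Study Design item c): depend on visible upset or on the family calling.
- Crisis and referral protocols, and the data collector's procedure for obtaining help (Vulnerable Populations; Risks to Research Participants): content not given.
- Withdrawal when someone may be a danger to themselves or others (Withdrawal of Research Participants): needs an indication, and no source for it is named.

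Remote delivery leaves less room for staff to notice a problem. Study Design item h has families work through recorded sessions with tests before and after, although Setting also mentions phone or video contact.

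**5. Size of a remedy.** 30 adolescents × 3 surveys = 90 responses at most. The two follow-up surveys, where the gap mainly lies, account for 30 × 2 = 60 of them.

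**The case against.** The strongest reply is that the documents show an item is not named, and do not show that none exists. No instrument's items are reproduced. Forms outside the table also exist: the screening form, the online prescreener, and the tests around each session. Given the entry exclusion, the screening form is a plausible place for a suicide-risk question. The crisis and data-collector protocols may also hold item-level triggers and response times. All of this stands, and it is why the point concerns what the protocol identifies. It decides which remedy applies, naming an item or adding one, but it does not supply the missing link. A screening question would not cover the later surveys, and the protocol points to no item in any form.

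Three stronger readings are tempting and should not be drawn.

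- A reader might infer that no questionnaire in the study asks about ideation, or that the PHQ-8 does not. The documents give no item content, so this cannot be shown from them.
- A reader might infer that adolescents scoring 9 to 19 on the PHQ-8 fall outside the review, with 20 as the threshold for severe depression. The range 9 to 19 is only the eligibility window. The protocol ties no score to the review, and its wording leaves room for clinical judgement on any questionnaire.
- A reader might infer that suicide risk goes unmanaged. The entry exclusion and the provisions compared above are real safeguards, and they place the gap mainly at follow-up.

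It is also fair to say that the emailed link is tied to social distancing, and that some participants may already have finished. The consent section makes provision for people who have completed all activities. Both limit the reach of a change, but neither removes the need for one in surveys still to be given.

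**Conclusion.** The point holds in this form: the ideation half of a safety promise made four times has no identified input (0 of 20 adolescent questionnaire rows) and no stated time for reading remote answers. Because current suicide risk is excluded at entry, the exposure is mainly to ideation that emerges by 3 and 6 months.

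This should be corrected, but it is not a fatal flaw. Other safeguards exist, though none is stated to ask about ideation.

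The conclusion assumes that the table is the list of study measures, as the protocol says, and that no unseen item or separate procedure already closes the gap. If one does, the defect is one of documentation and the remedy is editorial. The number of adolescents who could be missed cannot be computed from the documents, and no estimate is offered.

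**What to change.** 1. If an existing survey item asks about ideation, name it in the measures table.
2. If none does, add one brief suicidal-ideation item to the adolescent survey at baseline, 3 and 6 months, for surveys still to be given.
3. State that a positive answer goes to the psychologist review already promised.
4. State a prompt review time for responses that arrive through the emailed link.

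Any severity threshold on the PHQ-8, and the clinical response itself, are for the study's clinical team to set. The promised review can also lead to a referral for the parent, so that team should decide whether the parent survey needs the same treatment.

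The cost is a small added burden (at most 90 adolescent responses, fewer if some surveys are already complete), prompt checking of those responses, and an IRB amendment. The documents do not state the psychologist's availability for prompt checking, so it needs confirming before a time is written in. Randomisation, sample size, outcomes and analysis are unchanged.
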